### **4.3 Study endpoints**

#### **4.3.1 Primary endpoints**

- To assess survival at 1 year for patients treated with IMP.
- To assess event free survival at 1 year for patients treated with IMP.
  - To compare survival and event free survival at 1 year for patients treated with IMP compared to patients treated with allogeneic HSCT.
- Success of engraftment of transduced cells as assessed by vector copy number in the cells at each study visit.
- Reconstitution of cell mediated and humoral immunity as assessed by evidence of changes in T cell number, function and circulating immunoglobulin levels at each study visit.
- Correction of metabolic abnormalities as assessed by dATP and evidence of ADA activity in erythrocytes at each study visit compared to published data from HSCT treated patients

The following will be analysed at a specialist laboratory in Germany and the results reviewed and interpreted by the PI and the study team.

- Analysis of frequency of vector integration into known proto oncogenes
- Analysis of frequency of clonal expansion associated with vector integration near proto oncogene

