### **5.4 Concomitant medication**

Entry into this study will not affect concomitant treatments for ADA-deficiency, such as prophylactic antibiotics or intravenous gamma globulin therapy. However, the patient will be

withdrawn from cotrimoxazole prophylaxis at least day -1 prior to IMP infusion. Cotrimoxazole will be restarted when ANC > 1 x 10^9/l on 3 consecutive days after reinfusion of transduced cells. Aerosolised or intravenous pentamidine will be used as prophylaxis for *Pneumocystis jirovecii* in the intervening time period.

PEG-ADA will be continued until one month (+/- 6 days) post-infusion of gene-modified cells. PEG-ADA will be restarted if i) the child is withdrawn from the study ii) if after 180 days there is no evidence of gene modified cell engraftment and/or failure of T cell recovery.

PEG-ADA may be restarted at PIs discretion prior to this time point on clinical grounds e.g infective problems or delayed T cell reconstitution.

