### **8.2.1 Pre-treatment investigations**

Pregene therapy visit will be carried out prior to gene therapy. This visit will include pre-treatment monitoring investigations, which should be carried out within 3 months of the start of gene therapy treatment according to Appendix 5

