### **8.2.15 Transplant Details for the HSCT Controls**

For the HSCT control groups, the age in months at transplant will be recorded on the eCRF.

Age (months) at transplant, number of CD34+ cells/kg transplanted and busulfan dose, if appropriate, will be summarized for each HSCT control group using descriptive statistics.

Number (%) of subjects with each type of transplant cells, transplant donor type, conditioning type, receiving enzyme replacement therapy (ERT) prior to the transplant, receiving ERT after the transplant, receiving IgRT prior to the transplant, receiving IgRT after the transplant and receiving gene therapy after the transplant will be summarized for each HSCT control group.

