### **8.3.1.5 RBC ADA Enzyme Activity and Reduction in dATP**

RBC ADA enzyme activity, dATP and plasma deoxyadenosine will be summarized by visit for each of the IMP treated groups using descriptive statistics. The median value and range will be plotted by treatment group over time on a logarithmic scale. In addition, individual subject plots will be created.

Changes from baseline in each of the parameters will be calculated with baseline being the pre-treatment evaluation. The change from baseline will be summarized by visit for each of the IMP treated and HSCT control groups (data permitting) using descriptive statistics and 95% confidence intervals.

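### For metabolic correction, the SAP tabulates the HSCT controls only as change from a baseline that ignores PEG-ADA status, so the dATP and deoxyadenosine contrast with gene therapy depends on who was on enzyme at baseline

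*SAP*

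**What the plan says.** Protocol 4.3.1 makes correction of the metabolic defect a primary endpoint, assessed by dATP and red-cell ADA activity "at each study visit compared to published data from HSCT treated patients".

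SAP 8.3.1.5 carries this out in three steps.

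- Levels: "RBC ADA enzyme activity, dATP and plasma deoxyadenosine will be summarized by visit for each of the IMP treated groups using descriptive statistics". HSCT controls are not named.
- Plot: "The median value and range will be plotted by treatment group over time on a logarithmic scale". The groups are not listed.
- Change: "Changes from baseline in each of the parameters will be calculated with baseline being the pre-treatment evaluation". Then: "The change from baseline will be summarized by visit for each of the IMP treated and HSCT control groups (data permitting"), with descriptive statistics and 95% confidence intervals.

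On timing and background enzyme, Protocol 8.2.1 places the pre-treatment investigations for gene-therapy patients in a window "which should be carried out within 3 months of the start of gene therapy treatment". Protocol 5.4 states: "PEG-ADA will be continued until one month (+/- 6 days) post-infusion of gene-modified cells". For controls, SAP 8.2.15 counts those "receiving enzyme replacement therapy (ERT) prior to the transplant". Section 8.3.1.5 has no condition, stratification or adjustment for enzyme status at baseline.

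**The concern.** The endpoint asks whether gene therapy detoxifies as well as a transplant does. That is a question about the state reached at each visit. Protocol 8.4 also treats detoxification as a level: a sustained red-cell dATP below 250 umol/l is one of the factors for staying off PEG-ADA.

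The only table that shows both groups reports how far each has moved from its own starting point, and the starting points need not be comparable. Protocol 3.2.2 says that enough circulating ADA can return metabolites in deficient cells to normal. A child sampled on PEG-ADA therefore has less dATP and deoxyadenosine left to lose than a child sampled off it. Gene-therapy patients who are on PEG-ADA stay on it through infusion, so their baselines are on-enzyme values. Enzyme use among controls before transplant is treated as a variable and only counted.

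Change from baseline also loses data. A control with follow-up values but no metabolite result before transplant drops out. Protocol Appendix 8 says this information is available only from patients' records, for transplants going back to 2000.

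At stake is the between-group reading of a primary endpoint. The same end state in both groups could appear as a deficit or an advantage for gene therapy.

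**Working it through.** The plan gives no effect size, standard deviation or power for this endpoint, so there is no figure of its own to reproduce. The check is algebraic, followed by an illustration.

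**Notation**

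- F: achieved dATP, set equal in both groups
- U: mean dATP off PEG-ADA
- P: mean dATP on PEG-ADA
- q: share of IMP patients on PEG-ADA at baseline
- p: share of HSCT controls on PEG-ADA at baseline

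**Formulas**

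- IMP mean reduction = qP + (1 − q)U − F
- HSCT mean reduction = pP + (1 − p)U − F
- HSCT minus IMP = (q − p)(U − P)

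F cancels. The true difference in achieved level is F − F = 0, so any non-zero result is an artefact of the baselines. U is above P, so the sign is the sign of q − p.

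**Illustration.** None of U, P, q, p and F is in the documents; all are assumed. Take U = 1000, P = 200, F = 100 umol/l and q = 1.

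- IMP reduction: 200 − 100 = 100
- HSCT, p = 0: 1000 − 100 = 900, gap 800
- HSCT, p = 0.5: 0.5 × 200 + 0.5 × 1000 − 100 = 500, gap 400
- HSCT, p = 1: 200 − 100 = 100, gap 0

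**Range.** With U from 500 to 1500 and P from 100 to 200, U − P runs from 300 (500 − 200) to 1400 (1500 − 100).

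| q | p | q − p | Gap at U − P = 300 | Gap at U − P = 1400 |
|---|---|---|---|---|
| 1.0 | 0 | 1.0 | 300 | 1400 |
| 1.0 | 0.5 | 0.5 | 150 | 700 |
| 1.0 | 1.0 | 0 | 0 | 0 |
| 0.8 | 0.5 | 0.3 | 90 | 420 |
| 0.8 | 1.0 | −0.2 | −60 | −280 |

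Gaps are in umol/l. A positive gap means that gene therapy appears to reduce dATP less than HSCT although the end states are identical.

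**Plasma deoxyadenosine.** The same formula applies, with its own U and P.

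**Red-cell ADA activity.** Protocol 3.2.2 says the PEG coupling is meant to limit uptake of the enzyme by cells. If PEG-ADA does not raise red-cell activity, on- and off-enzyme baselines coincide, U − P is 0 and so is the artefact.

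**The case against.** A reader might infer that the planned comparison is biased against gene therapy. The documents do not support that. The sign depends on q − p, which is not given. Planning to count prior enzyme use in controls does not show that some went without it; SAP 8.2.3 plans the same count for gene-therapy patients. Protocol 9.2.5 says most, not all, of the trial's patients will have received PEG-ADA. The primary control group in SAP 7.1 is patients without a matched family donor, and Protocol 3.2.2 describes patients lacking a matched related donor as those who were given PEG-ADA first. The shares may therefore be close in the primary comparison. They may differ more against matched-related-donor controls.

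A reader might also infer that control levels will never be shown. That goes too far, because the plot may include them. In SAP 8.2.16, 8.3.1.1 and 8.3.2.3 the term treatment group covers HSCT controls. In 8.3.1.4 the same plotting sentence follows a summary of IMP groups alone. The plot is ambiguous, not an exclusion.

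The stated objectives (Protocol 4.2.1, SAP 4.1) speak of a reduction in dATP, so change from baseline is a legitimate summary. The IMP levels needed for a comparison with published data are tabulated. The HSCT comparisons listed in SAP 6 and Appendix 8 concern survival, event-free survival, immunoglobulin use and infections. The metabolic summary is descriptive and depends on data being available.

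Finally, levels alone could mislead too. SAP 8.2.15 counts controls who received enzyme after transplant, and a failed transplant back on PEG-ADA could show a low dATP. On-study gene-therapy patients who restart are, under Protocol 4.1 and 8.4, to be withdrawn.

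All of this stands as a limit on the point and shapes the fix. None of it makes an unadjusted change from baseline a sound way to compare detoxification. SAP 8.3 also says its IMP-versus-HSCT comparison applies to all efficacy analyses, which include this endpoint.

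**Conclusion.** The point holds in conditional form. HSCT controls are tabulated only as change from a baseline that takes no account of PEG-ADA. For dATP and plasma deoxyadenosine the resulting contrast is shifted by (q − p)(U − P) when true correction is equal. The shift understates gene therapy if fewer controls than IMP patients were on enzyme, vanishes if the shares match, and favours gene therapy if more controls were on enzyme.

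The illustrative sizes, up to 1400 umol/l one way and 280 the other, rest wholly on assumed levels and shares and should not be read as estimates for this trial. Red-cell ADA activity, the other part of the endpoint, is little affected provided PEG-ADA does not enter red cells. Because the analysis is descriptive, no error rate is at stake. The risk is a misleading description of a primary endpoint, and it is cheap to remove.

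**What to change.** In SAP 8.3.1.5:

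- Tabulate achieved red-cell ADA activity, dATP and plasma deoxyadenosine by visit for each HSCT control group beside the IMP groups, data permitting, taking the nearest value in a stated window. Use these levels for the IMP-versus-HSCT description.
- Show enzyme status at the time of each sample and report on-enzyme values separately, in both groups.
- Keep change from baseline, but split it by PEG-ADA status at baseline for both IMP and HSCT groups.
- State which groups the level plot covers.
- Optionally, add the proportion with dATP below 250 umol/l as a descriptive line.

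Also reconcile the comparator: Protocol 4.3.1 names published HSCT data, whereas the SAP uses the GOSH cohort.

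The cost is SAP wording and one extra table. Appendix 8 already plans to collect ADA activity, metabolites and previous PEG-ADA with its duration; enzyme status at each control sample would have to be taken from the same records. Controls without a pre-transplant value become usable for the level table. The drawback is that control data will be sparse at some visits.

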## **8.3.2 Secondary Efficacy Endpoints**

### **8.3.2.1 Overall and Event-free Survival at 2 and 3 Years**

Overall and event-free survival at 2 and 3 years will be summarized in the same way as for the analyses at 12 months described in Sections 8.3.1.1 and 8.3.1.2.

### 8.3.2.2 Use of Immunoglobulin Replacement Therapy

The time to cessation of IgRT will be calculated (in months) as:

$12 * (\text{stopping date of IgRT} - \text{date of transplant}) / 365.25$ ,

or, for HSCT control subjects for whom the dates were not recorded, as:

age in months when IgRT stopped – age in months at transplant.

Time to cessation of IgRT will be summarised for each of the IMP treated and HSCT control groups using descriptive statistics and, if appropriate, estimated from a Kaplan-Meier curve in which subjects who are still receiving IgRT will be censored at the time of their last visit.

The number (%) of subjects who have stopped treatment with IgRT at 12, 18, 24, 30 and 36 months without restarting at any subsequent time point will be summarized for each of the IMP treated and HSCT control groups (data permitting) along with exact 95% CIs.

In addition, serum immunoglobulin levels (IgG, IgA and IgM) will be measured at each visit for the IMP treated subjects. Levels of IgG, IgA and IgM and changes from baseline will be summarised by visit using descriptive statistics. In addition, plots of the median value and range over time on a logarithmic scale will be produced for each parameter along with individual plots for each subject which will include age-dependent normal ranges provided by the study site.

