### Main Secondary Endpoint

Percentage of subjects requiring immunoglobulin replacement therapy will be provided for each cohort (See Overview Section above) along with associated, two-sided, exact binomial, 95% confidence intervals.

The detailed statistical procedures will be provided in the statistical analysis plan (SAP).

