## Appendix 8: Details of the historical HSCT control group

### 1. Objective

Historical data from ADA-SCID patients who were treated with Hematopoietic Stem Cell Transplantation (HSCT) at GOSH during the period of 2000-2016 will be collected. HSCT is currently the standard of care for ADA-SCID patients. These data will be used as historical control group in a current on-going gene therapy study “Phase I/II, historical controlled, open-label, non-randomised, single-centre trial to assess the safety and efficacy of EF1αS-ADA lentiviral vector mediated gene modification of autologous CD34+ cells from ADA-deficient individuals”. The objective is to compare efficacy and safety of gene therapy versus HSCT to determine the optimal treatment.

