## 6 Timing of Analyses

The statistical analyses of data from this study will be performed in four stages:

Interim look:

- Performed after all on-study subjects have completed 6 months of follow-up post infusion
- Descriptive statistics for all available data

- Comparisons between IMP treated subjects and HSCT control cohorts of demographics and overall survival

Primary analysis:

- Performed after all on-study subjects have completed 12 months of follow-up post infusion
- Descriptive statistics for all available data
- Comparison to HSCT control cohorts on overall and event-free survival at 12 months (primary efficacy endpoints), use of immunoglobulin replacement therapy (IgRT) and infection rate (key secondary endpoints).

Long-term follow-up analysis:

- Performed after all on-study subjects have completed 2 years of follow-up post infusion
- Descriptive statistics for all available data
- Comparison to HSCT control cohorts on overall and event-free survival at 2 years, use of immunoglobulin replacement therapy (IgRT) and infection rate (key secondary endpoints).

End of study analysis:

- Performed after all on-study subjects have completed the study (3 years of follow-up post infusion)
- Descriptive statistics for the complete study cohort
- Comparison to HSCT control cohorts on overall and event-free survival at 3 years, use of immunoglobulin replacement therapy (IgRT) and infection rate (key secondary endpoints).

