## **8 Statistical Methods**

In general, continuous variables will be summarised using the mean, standard deviation, median, minimum, maximum and number of subjects. Categorical variables will be summarised using number of subjects and percentages.

For all summaries, the IMP treated subjects will be summarised in the groups of on-study only and on-study plus CUP subjects. The HSCT controls will be summarised in the groups of those without a matched related donor, those with a matched related donor and all subjects.

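### SAP 8.3.2.2: IMP and HSCT times to stopping immunoglobulin replacement are described among stoppers only, with no common follow-up horizon, so their means and medians are not comparable

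*SAP*

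**What the plan says.** - SAP section 6 lists "use of immunoglobulin replacement therapy (IgRT) and infection rate (key secondary endpoints" among the comparisons with the HSCT cohorts at the 12-month, 2-year and 3-year analyses.
- SAP 8.3.2.2 begins: "The time to cessation of IgRT will be calculated (in months) as" stop date minus transplant date. For controls without dates it uses age at stopping minus age at transplant.
- The unconditional summary comes next in that section: "Time to cessation of IgRT will be summarised for each of the IMP treated and HSCT control groups using descriptive statistics and, if appropriate".
- The conditional part of the same sentence is a second estimate, which the SAP describes as "estimated from a Kaplan-Meier curve in which subjects who are still receiving IgRT will be censored at the time of their last visit".
- SAP section 8 defines the descriptive part: "continuous variables will be summarised using the mean, standard deviation, median, minimum, maximum and number of subjects".
- SAP 8.3.2.2 also gives, for both groups (data permitting for HSCT), the number and percentage who have "stopped treatment with IgRT at 12, 18, 24, 30 and 36 months without restarting at any subsequent time point", with exact 95% confidence intervals.
- The protocol's main secondary endpoint, in section 8.9.2, is a percentage: "Percentage of subjects requiring immunoglobulin replacement therapy will be provided for each cohort".
- Follow-up differs by group. The protocol summary ends each on-study child's participation 3 years after infusion. Protocol Appendix 8 says that HSCT data "during the period of 2000-2016 will be collected". SAP 8.2.16 takes the length of HSCT follow-up from the eCRF. Neither document states a cut-off for HSCT stopping times.

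**The concern.** A child still on immunoglobulin has no stop date and so no value of the variable. The SAP does not say that such children are left out, but the derivation allows nothing else. The mean, median and range therefore describe stoppers only, and they depend on how long each group was watched. A 36-month limit removes every late stop from the on-study IMP group, while a control followed for ten years can contribute a stop at year eight.

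The Kaplan-Meier estimate would handle this, but it is conditional and no criterion is given. For overall survival, by contrast, SAP 8.3.1.1 makes the Kaplan-Meier curve unconditional.

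At stake is a side-by-side display in which IMP children seem to come off immunoglobulin sooner only because their follow-up is shorter.

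**Working it through.** The plan gives no expected stopping time, rate or power for this variable, so there is no figure of its own to reproduce. The check asks what the descriptive statistics would show if both groups had the same true distribution.

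**Inputs from the documents.** On-study IMP follow-up of 36 months at study end; 10 on-study children (SAP 7.1); HSCT transplants 2000-2016.

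**Assumptions, not in the documents.** Exponential stopping times with a true median of 18 or 24 months in both groups; no deaths; HSCT follow-up spread evenly over 12-72 months (short case) or 24-200 months (long case).

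**IMP, all followed to c = 36.** Let λ = ln 2 / median and F = 1 − exp(−λc), the share who have stopped.

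- Mean among stoppers = 1/λ − c·exp(−λc)/F
- Median among stoppers = −ln(1 − F/2)/λ

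True median 18: λ = 0.0385, F = 0.75. Mean = 25.97 − 36 × 0.25/0.75 = 14.0. Median = 0.470/0.0385 = 12.2.

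True median 24: λ = 0.0289, F = 0.646. Mean = 34.62 − 36 × 0.354/0.646 = 14.9. Median = 0.390/0.0289 = 13.5.

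**HSCT, follow-up even on a to b.** The density of observed stops is proportional to λ·exp(−λt)·G(t). G(t) is the share followed at least to t: 1 up to a, then (b − t)/(b − a). Numerical integration gives the HSCT columns, in months.

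| True median, both groups | IMP children with no value | IMP mean / median | HSCT 12-72: mean / median | HSCT 24-200: mean / median |
|---|---|---|---|---|
| 18 | 25% | 14.0 / 12.2 | 15.8 / 12.3 | 22.9 / 16.5 |
| 24 | 35% | 14.9 / 13.5 | 17.6 / 14.0 | 28.4 / 20.8 |

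The spurious gap in means is about 2 to 3 months in the short case and about 9 to 13.5 months in the long case. In medians it is 0.1 to 0.5 and 4.3 to 7.3 months.

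**Sensitivity.**

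- True median 9, long case: medians 8.2 (IMP) and 8.8 (HSCT). True median 48, long case: 15.7 and about 32.
- Stopping times more concentrated (Weibull shape 2, true median 18, long case): medians 17.2 and 17.8.
- Truly slower IMP (true medians 36 for IMP, 18 for HSCT, long case): observed medians 14.9 and 16.5, so the slower group looks faster.
- Both groups cut at 36 months: no gap.

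**Does censoring repair it?** Trials were simulated with 10 IMP and 15 HSCT children (the 15 is assumed), identical true distributions and the long case. The mean Kaplan-Meier probability of stopping by 24 months was 0.748 (IMP) and 0.752 (HSCT) at true median 12, 0.501 and 0.503 at 24, and 0.374 and 0.372 at 36. The IMP Kaplan-Meier median could not be estimated in 9% of trials at true median 24 and in 37% at 36. The cumulative proportion at common times is therefore the safer summary.

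**The case against.** The strongest reply is that the plan already contains a better analysis. The proportions stopped at 12, 18, 24, 30 and 36 months keep children still on immunoglobulin in the count, use common time points and carry exact intervals. They are the counterpart of the protocol's main secondary endpoint, which is a percentage. SAP section 6 gives key status to use of immunoglobulin, not to time to cessation, and no test of the times is planned. The Kaplan-Meier clause does censor children still on treatment, and the descriptive statistics include the number of subjects. All of this stands. A reader might infer that the key comparison itself drops every child still on treatment; the documents do not support that.

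A reader might also infer a gap of 19 to 25 months at the primary analysis. That follows from cutting every IMP child at 12 months (means 5.5 and 5.7 at true medians 18 and 24) and following every control for 120 months (24.8 and 30.8). But 12 months is the minimum at that analysis, and all available data are used. With even accrual over the planned 5-year recruitment, follow-up would run from 12 months up to the 36-month cap, and the IMP means would be 12.8 and 13.6. Nor can 120 months be assumed for all controls: at the SAP date of January 2018, a child transplanted after January 2008 had less.

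The reply does not remove the point. The proportions stand beside the observed times without replacing them, and for HSCT they depend on the data permitting. Their no-later-restart condition also depends on length of follow-up, in that case against the longer-followed HSCT group. Section 8.3.2.2 has no rule for a child who has not yet reached a time point, whereas SAP 8.3.1.1 gives such a child unknown status for survival.

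**Conclusion.** The point holds as a defect in one planned summary. Followed as written, SAP 8.3.2.2 produces IMP and HSCT means and medians that depend on length of follow-up. They favour IMP if HSCT follow-up is longer. The protocol's percentage endpoint is not affected by this.

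The size is conditional. For true medians of 18 to 24 months and exponential stopping, the gap in medians runs from under 1 month to about 7, and the gap in means from about 2 months to about 13.5. The result turns on HSCT follow-up and on the true stopping pattern, and the documents give neither. It would go too far to say that identical groups must look very different: with short HSCT follow-up or concentrated stopping times they look nearly alike. The change is still worth making because it is cheap and removes the dependence on follow-up.

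**What to change.** In SAP 8.3.2.2:

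1. Make the cumulative proportion who have stopped the stated summary, without a condition, for all subjects on immunoglobulin at treatment. Estimate it by Kaplan-Meier, or by cumulative incidence if death is treated as a competing event. Cut both groups at 12, 24 and 36 months at the successive analyses.
2. Do not compare mean or median observed stopping times between groups. If they are listed, restrict them to stops within the same horizon and print the number not stopped beside them.
3. State how death, second transplant and restarting immunoglobulin are handled, since the present censoring rule covers only children still receiving it. For the proportions at fixed times, state what happens to a child who has not reached the time point, and limit the no-restart condition to the common horizon.

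The cost is a few sentences and a cut-off in the program, with no new data. The downside is that HSCT stops after 36 months leave this comparison; they can still be described for the HSCT group alone.

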#### **4.2.2 Secondary objectives**

The secondary objectives are to:

- Compare survival and event free survival at 2 and 3 years between patients treated with IMP and patients treated with allogeneic HSCT
- Determine the percentage of IMP treated patients requiring immunoglobulin replacement therapy at all evaluation points from 18 months onwards
- Compare frequency of infections, and growth of pathogenic microorganisms over 3 years
- Evaluate the longitudinal clinical effect in terms of improved immunity
- Evaluate tolerability of conditioning regimen. These data will be reviewed and interpreted by the PI and the study team
- Evaluate feasibility of the transduction procedure. These data will be reviewed and interpreted by the PI and the study team

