#### **4.3.2 Secondary endpoints**

- 1) Survival and Event free survival at 2 years and 3 years
- 2) Reduction in frequency of infections (evaluated at 1, 2 and 3 years after treatment based on clinical history and examination)
- 3) Long term immune reconstitution as assessed by sustained improvement in thymic function assessed by TRECS after 2 years post-gene therapy
- 4) Serum immunoglobulin levels for IgA, IgG and IgM and patients requiring immunoglobulin replacement therapy (recorded dichotomously).
- 5) Feasibility of the transduction procedure assessed by availability of greater than  $0.5 \times 10^6$  CD34+ cells/kg after transduction; undetectable RCL (determined retrospectively); and CD45+ cell viability after transduction equal to or greater than 50%, in accordance with the final product release criteria. These data will be reviewed and interpreted by the PI and the study team.

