## 5.2 Secondary Endpoints

- Overall survival and event-free survival at 2 years and 3 years
- Frequency of infections (evaluated at 1, 2 and 3 years after treatment)
- TRECS after 2 years post-gene therapy
- Requirement for immunoglobulin replacement therapy (IgRT) and serum immunoglobulin levels for IgA, IgG and IgM.
- Feasibility of the transduction procedure assessed by availability of greater than  $0.5 \times 10^6$  CD34+ cells/kg after transduction; undetectable RCL (determined retrospectively); and CD45+ cell viability after transduction equal to or greater than 50%, in accordance with the final product release criteria. These data will be reviewed and interpreted by the PI and the study team and so will not be included in this SAP.

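### The main secondary endpoint is the percentage requiring immunoglobulin replacement, but the SAP analyses the percentage that have stopped it, with no denominator and no rule for deaths, never-users or unknown status

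*SAP*

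**What the plan says.** Protocol 8.9.2 (Main Secondary Endpoint) states: "Percentage of subjects requiring immunoglobulin replacement therapy will be provided for each cohort", with "two-sided, exact binomial, 95% confidence intervals". The objective in protocol 4.2.2 concerns gene therapy (IMP) patients "requiring immunoglobulin replacement therapy at all evaluation points from 18 months onwards". Protocol 4.3.2 lists the requirement as a yes/no item. SAP 4.2 and SAP 5.2 repeat the same concept.

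The analysis section, SAP 8.3.2.2, tabulates something else: "The number (%) of subjects who have stopped treatment with IgRT at 12, 18, 24, 30 and 36 months", with the added condition "without restarting at any subsequent time point", for the IMP and HSCT groups as data permit, with exact 95% intervals. It also plans time to cessation of IgRT, with a Kaplan-Meier curve that censors children still on treatment at their last visit. That section contains no table of the percentage requiring IgRT.

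SAP 6 makes IgRT use a key secondary comparison with HSCT at the 12-month, 2-year and 3-year analyses. SAP 8.3 sets the primary comparison for all efficacy analyses as on-study IMP children against HSCT controls without a matched related donor.

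**The concern.** The analysis as written does not produce the stated endpoint, and the inconsistency lies within the SAP as well as between the two documents. It would be harmless if *stopped* were simply one minus *requiring*. That holds only if every child counted is alive, assessed and was on IgRT at some point.

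Neither document states the denominator, or how to count a child who dies, was never on IgRT or has unknown status. For overall survival, by contrast, SAP 8.3.1.1 does say what happens to unknown status.

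The gap could matter for the comparison because mortality may differ between the groups. The protocol's background cites survival of about two thirds, 43% and 29% after matched unrelated, haploidentical and mismatched unrelated transplants (3.2.1), against 100% in earlier gene therapy (Table 1). Protocol 3.2.1 places most deaths with these donor types in the first 100 days, before any IgRT landmark.

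The no-restart condition is a further departure. It makes a child's month-12 status depend on what happens later, and later follow-up is unlikely to be equal: controls date from 2000 onwards, while on-study follow-up is three years.

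**Working it through.** The documents give no sample size, power or target rate for this endpoint, so there is no figure of the plan's own to reproduce. The check is algebra plus exact (Clopper-Pearson) 95% intervals.

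**Scoring with all treated children as denominator**

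| Child at the landmark | Counted as requiring? | Counted as stopped? | Complementary? |
|---|---|---|---|
| Alive, on IgRT | yes | no | yes |
| Alive, stopped | no | yes | yes |
| Died on IgRT | no (favourable) | no (unfavourable) | no |
| Never on IgRT | no (favourable) | no (unfavourable) | no |

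**When the direction differs.** Let d be the share of HSCT children who die on IgRT, pH the share of HSCT survivors requiring IgRT, and pI the share of IMP children requiring it, with no IMP deaths.

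- *Requiring* compares pI with (1−d)pH. It favours HSCT if pI > (1−d)pH.
- *Stopped* compares 1−pI with (1−d)(1−pH). It favours IMP if pI < d + (1−d)pH.
- The two disagree when (1−d)pH < pI < d + (1−d)pH, a window of width d.

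**Inputs for the illustration**

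- IMP: 10 on-study children (SAP 7.1), assumed all alive, 5 off IgRT and 5 requiring it. The rate is borrowed from an earlier gene therapy series of ten, in which five children discontinued immunoglobulin (protocol 3.2.5).
- HSCT: 15 treated, 5 dead on IgRT and 10 alive, patterned on the matched unrelated donor figure in protocol 3.2.1 (10/15 = 67%; the protocol prints 66% there and 67% in 5.1.3). This is an assumption. The GOSH control size and mortality are not given.
- HSCT survivors: 4 of 10 requiring IgRT, assumed, then varied.

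**Results**

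| Measure | IMP | HSCT | Favours |
|---|---|---|---|
| Requiring, all treated | 5/10 = 50.0% (18.7 to 81.3) | 4/15 = 26.7% (7.8 to 55.1) | HSCT |
| Stopped, all treated | 5/10 = 50.0% (18.7 to 81.3) | 6/15 = 40.0% (16.3 to 67.7) | IMP |
| Requiring, survivors ever on IgRT | 50% | 4/10 = 40% | HSCT |
| Stopped, survivors ever on IgRT | 50% | 6/10 = 60% | HSCT |

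In the formula, d = 1/3 and pH = 0.4 give a window from (2/3)(0.4) = 0.27 to 1/3 + 0.27 = 0.60, and pI = 0.5 lies inside it.

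**Range.** With these group sizes the all-treated directions differ when 3 to 7 of the 10 HSCT survivors require IgRT, and agree for 0 to 2 and 8 to 10. Holding pI at 0.5, the reversal range of pH is:

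- d = 0.10: about 0.44 to 0.56
- d = 0.20: 0.375 to 0.625
- d = 1/3: 0.25 to 0.75
- d = 0.57 (43% survival): every value

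**Never-users alone.** Suppose no deaths; IMP 4 requiring and 6 stopped of 10; HSCT 3 never on, 5 requiring and 7 stopped of 15. *Requiring* is 40.0% v 33.3% (favours HSCT) and *stopped* is 60.0% v 46.7% (favours IMP).

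**The case against.** The strongest reply is that the opposite scoring is a consequence of one denominator, and no section prescribes it. A reader might infer that the protocol counts a dead child as a success for not requiring IgRT. It does not say so. Among survivors ever on IgRT the two wordings agree. This stands: the supported finding is an endpoint that is not analysed plus an unstated denominator, and the reversal is a possibility rather than a planned result.

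Other parts of the reply also stand:

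- Never-users are probably few. "receiving IgRT prior to the transplant, receiving IgRT after the transplant" in SAP 8.2.15 shows that IgRT use is counted, not that some children never had it, and protocol 3.1.6 says immunoglobulin is started at diagnosis. Deaths are the main route.
- A reader might infer that deaths will fall almost wholly among the controls. The cited transplant series is multicentre, whereas the controls are GOSH only, so their mortality is unknown.
- The time points do not conflict. The SAP's visits cover every scheduled one from month 18, and month 12 serves the 12-month comparison in SAP 6.
- The comparisons with HSCT are described as descriptive (protocol 8.9.2), and the intervals are wide. What can change is the sign of a point estimate, not a test result.

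One part does not stand. Protocol 8.9.2 leaves detailed procedures to the SAP, and stopping without restart is a plausible way to operationalise the requirement. But the SAP does not say that it is doing so, and its own objective and endpoint list still name the requirement. The Kaplan-Meier analysis does not fill the gap, since it has no separate rule for death.

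**Conclusion.** The point holds in a limited form, and the plan should be corrected on it. The stated main secondary endpoint is not the quantity tabulated, and the substitute is its complement only among children alive, assessed and ever on IgRT.

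If all treated children are the denominator, the direction of the IMP-versus-HSCT point estimates can depend on the wording. In the illustration the difference moves from 23 points favouring HSCT (50.0 − 26.7) to 10 points favouring IMP (50.0 − 40.0). This rests on an assumed 50% IMP rate, an assumed HSCT group of 15 with one third dead on IgRT, and no IMP deaths. With few control deaths the window is narrow. With a denominator of survivors ever on IgRT it closes.

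The documents do not support saying that the comparison will reverse. They leave open a choice that could reverse it, in an open-label trial whose control data are meant to support marketing authorisation (protocol Appendix 8).

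**What to change.** Use one definition in both documents. At each landmark and for each cohort, classify every treated child with enough elapsed follow-up into one of four states, using status at that landmark rather than later restarts: alive and off IgRT (including never started), alive and on IgRT, dead, or unknown.

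From that table report, with exact 95% intervals:

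- the percentage requiring IgRT among children alive with known status, which is the protocol endpoint (50% v 40% in the illustration);
- the percentage alive and off IgRT among all treated (50% v 40%).

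Show deaths beside both, and state in advance which measure leads. The example shows why: the first pair favours HSCT and the second favours IMP, and the four-state table makes plain that the deaths account for the difference. Which should lead is a choice of estimand. The all-treated figure mixes in mortality that overall survival already measures.

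The SAP time points can stay, with month 12 labelled as additional to the objective of 18 months onward.

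The cost is SAP wording and a few table rows. No new data appear to be needed: IgRT status is collected at follow-up (protocol Appendix 5), and death dates and immunoglobulin history are planned for the controls (Appendix 8).
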